3.4.4 Analysis of patient reported outcomes

For the analysis of quality of life assessments/patient reported outcomes (PRO), the scoring of the questionnaires will be handled as specified by the instrument developers.

To assess rate of missing data, a table of completion rates for each questionnaire at each scheduled assessment will be created. The table will include number of patients eligible for PRO assessment and number of patients with complete PRO assessment data, completion will be defined by each instruments scoring guidelines.

Change in individual scores/scales from baseline will be summarized descriptively at each visit. For FACT-Lymphoma scores, repeated measures analysis will also be used.

Change in ECOG Performance Status

The ECOG performance score will be summarized descriptively by visit. The summary will include the number and percent of patients at each reported value. A shift table including the number and percent of patients will also be produced by visit of baseline vs. post-baseline scores.

Change in FACT-Lym scores

The FACT-Lym questionnaire consists of a total of 42 questions contributing to 5 subscales (i.e., physical well-being, social/family well-being, emotional well-being, functional well-being and lymphoma subscale) which in turn contribute to three total sum scores, namely

FACT-Lym Trial Outcome Index (TOI), FACT-General (FACT-G) total score and FACT-Lym total score. More details on the questionnaire and derivation of the score can be found in Section 16.1.9.

Data from FACT-Lymphoma scores will be analyzed in the three sum scores and one subscale LymS. Change and percent change from baseline to each scheduled visit when the FACT-Lymphoma scores were collected will be calculated. The scores will be summarized descriptively by visit. The change from baseline score at each time point will be estimated by using repeated measurement analysis for patients with at least one post-baseline scale score. Patients without baseline value will not be considered in the analysis and baseline is the data collected from the last visit prior to or at Day1.

Time on treatment time will be treated as a discrete variable to allow for a nonlinear relationship between PRO scores and time. Time, DIPSS status and baseline score (as a covariate) will be included in the model as fixed effects, while the patient-specific intercept will be included as a random effect.

DIPSS status will be calculated as per the criteria given in section 3.11.3

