Appendix 16.1.9 Documentation of statistical methods

FACIT-Fatigue Scale questionnaire:

FACIT-Fatigue scale consists of a total of 13 items (an item is equivalent to a question); each item is scored on a scale of 0 to 4. For some questions, a reversal of the raw item score is required to make all item scores in the same direction: higher the score is, better the QOL is. For each raw item score where reversal is required, the reversal will always be calculated by:

$$\text{New Item Score} = 4 - \text{Raw Item Score}$$

Based on the 13 individual item scores, the total score will be derived:

FACIT- Fatigue total score = sum of all the individual scores

FACIT-Fatigue scoring guidelines

Instructions:

1. Record answers in "item response" column. If missing, mark with an X.
2. Perform reversals as indicated, and sum individual items to obtain a score.
3. Derive total score.
4. The higher the score, the better the QOL.

The FACIT-Fatigue Scale questionnaire consists of the following 13 questions.

1. I feel fatigued
2. I feel weak all over
3. I feel listless ("washed out")
4. I feel tired
5. I have trouble starting things because I am tired
6. I have trouble finishing things because I am tired
7. I have energy
8. I am able to do my usual activities
9. I need to sleep during the day
10. I am too tired to eat
11. I need help doing my usual activities
12. I am frustrated by being too tired to do the things I want to do
13. I have to limit my social activity because I am tired

FACT-Lymphoma questionnaire

FACT-Lymphoma questionnaire consists of a total of 42 questions; each question takes an item score of 0 to 4. For some questions, a reversal of the raw item score is required to make all item scores in the same direction: higher the score is, better the QOL is. For each raw item score that the reversal is required, the reversal will always be calculated by

$$\text{New Item Score} = 4 - \text{Raw Item Score}$$

Based on the 42 individual item scores, the following 5 subscales will be derived:

1. **Physical Well-Being (PWB)**: it is the mean of non-missing individual item scores from Questions GP1, GP2, GP3, GP4, GP5, GP6, and GP7 multiplied by 7, where each item score is the reverse of the raw item score.
2. **Social/Family Well-Being (SWB)**: it is the mean of non-missing individual item scores from Questions GS1, GS2, GS3, GS4, GS5, GS6, and GS7 multiplied by 7.

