3. **Emotional Well-Being (EWB)**: it is the mean of non-missing individual item scores from Questions GE1, GE2, GE3, GE4, GE5, and GE6 multiplied by 6, where each item score is the reverse of the raw item score except for the 2nd item score from Question GE2.
4. **Functional Well-Being (FWB)**: it is the mean of non-missing individual item scores from Questions GF1, GF2, GF3, GF4, GF5, GF6 and GF7 multiplied by 7.
5. **Lymphoma Subscale (LymS)**: it is the mean of non-missing individual item scores from Questions P2, LEU1, BRM3, ES3, LYM1, LYM2, BMT6, C2, GA1, H18, N3, LEU6, LEU7, BRM9, and LEU4 multiplied by 15, where each item score is the reverse of the raw item score.

A subscale will be missing if the corresponding item scores are all missing. Based on the 5 subscale scores, the following 3 total scores will be calculated:

- FACT-Lymphoma Trial Outcome Index (TOI) = PWB + FWB + LymS
- FACT-G total score = PWB + SWB + EWB + FWB
- FACT-Lymphoma total score = PWB + SWB + EWB + FWB + LymS

A total score will be missing if any of the corresponding subscales is missing.

FACT-Lymphoma scoring guidelines

Instructions:

5. Record answers in "item response" column. If missing, mark with an X.
6. Perform reversals as indicated, and sum individual items to obtain a score.
7. Multiply the sum of the item scores by the number of items in the subscale, then divide by the number of items answered. This produces the subscale score.
8. Add subscale scores to derive total scores (TOI, FACT-G & FACT-Lymphoma).
9. The higher the score, the better the QOL.

Subscale	Item code	Reverse item?	Item response	Item score
PHYSICAL WELL-BEING (PWB) Score range: 0-28	GP1	4	—	= _____
	GP2	4	—	= _____
	GP3	4	—	= _____
	GP4	4	—	= _____
	GP5	4	—	= _____
	GP6	4	—	= _____
	GP7	4	—	= _____

Sum individual item scores: _____

Multiply by 7: _____

Divide by number of items answered: _____ =PWB subscale score

SOCIAL/FAMILY WELL-BEING (SWB) Score range: 0-28	GS1	0	+	_____	= _____
	GS2	0	+	_____	= _____
	GS3	0	+	_____	= _____
	GS4	0	+	_____	= _____
	GS5	0	+	_____	= _____
	GS6	0	+	_____	= _____
	GS7	0	+	_____	= _____

Sum individual item scores: _____

Multiply by 7: _____

Divide by number of items answered: _____ =SWB subscale score

EMOTIONAL WELL-BEING (EWB) Score range: 0-24	GE1	4	—	_____	= _____
	GE2	0	+	_____	= _____
	GE3	4	—	_____	= _____
	GE4	4	—	_____	= _____
	GE5	4	—	_____	= _____
	GE6	4	—	_____	= _____

Sum individual item scores: _____

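### The SAP's FACT-Lym appendix scores a subscale from any number of answered items, and the SAP does not say whether this or the developers' missing-data instructions govern

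*SAP*

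**What the plan says.** SAP Appendix 16.1.9 defines each FACT-Lym subscale as a prorated mean. For physical well-being (PWB), "it is the mean of non-missing individual item scores from Questions GP1, GP2, GP3, GP4, GP5, GP6, and GP7 multiplied by 7". LymS is built the same way from 15 items: the text begins "it is the mean of non-missing individual item scores from Questions P2, LEU1, BRM3, ES3, LYM1, LYM2, BMT6, C2, GA1" and ends "BRM9, and LEU4 multiplied by 15, where each item score is the reverse of the raw item score". Scoring instruction 7 in the same appendix repeats the proration: "Multiply the sum of the item scores by the number of items in the subscale, then divide by the number of items answered". Neither place sets a minimum number of answers. The one stated condition for a missing subscale is "A subscale will be missing if the corresponding item scores are all missing". For the sum scores, "A total score will be missing if any of the corresponding subscales is missing".

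Two other places in the SAP point elsewhere. Section 3.4.4 says that questionnaire scoring follows the instrument developers. For the table of completion rates it adds that "completion will be defined by each instruments scoring guidelines". Section 3.11.1 says that missing quality-of-life values follow the instruments' own instructions. Section 3.4.4 also sends the reader to 16.1.9 for score derivation, and 16.1.9 contains the only FACT-Lym scoring rules written out in the documents.

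The responder table in SAP 3.4.4 gives cutoffs of 5.4 (LymS), 7 (FACT-G), 11 (Trial Outcome Index, TOI) and 11.2 (FACT-Lym total). An improvement equal to the cutoff counts as a response.

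**The concern.** Prorating assumes that the answered items can stand in for the unanswered ones. With one answer out of 15, that answer is multiplied by 15, and the score can take only the values 0, 15, 30, 45 or 60. On such a form the smallest possible change exceeds the cutoff that is meant to mark an important improvement.

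These scores feed four analyses in SAP 3.4.4: the descriptive summaries by visit, the repeated-measures model, the responder proportions, and the Kaplan-Meier estimate of time to first improvement. The last is the most exposed, because one high score at any visit is an event. The completion table may not reveal the problem. If the appendix is taken as the scoring guideline, a nearly empty form could count as complete.

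**Working it through.** **Inputs.** All come from SAP Appendix 16.1.9 and the responder table in SAP 3.4.4.
- Items per subscale: PWB 7, social/family (SWB) 7, emotional (EWB) 6, functional (FWB) 7, LymS 15.
- Item scores: "FACT-Lymphoma questionnaire consists of a total of 42 questions; each question takes an item score of 0 to 4", so one step is 1.
- Cutoffs (upper end of the minimally important difference, MID): LymS 5.4, FACT-G 7, TOI 11, FACT-Lym total 11.2.
- Lower end of the MID: LymS 2.9, FACT-G 3.

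**Reproducing the plan's ranges.** Maximum = items × 4.
- LymS: 15 × 4 = 60.
- TOI: 28 + 28 + 60 = 116.
- FACT-G: 28 + 28 + 24 + 28 = 108.
- FACT-Lym total: 108 + 60 = 168.

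All four agree with the SAP.

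**One-step change.** Subscale = (sum of item scores) × n / k, with n items in the subscale and k answered. If the same k items are answered at both visits, a one-step change in one of them moves the subscale by n/k. For LymS:

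| Items answered, k | 15/k | Reaches 5.4? | Reaches 2.9? |
|---|---|---|---|
| 1 | 15.0 | yes | yes |
| 2 | 7.5 | yes | yes |
| 3 | 5.0 | no | yes |
| 5 | 3.0 | no | yes |
| 6 | 2.5 | no | no |
| 8 | 1.875 | no | no |
| 15 | 1.0 | no | no |

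With all 15 items answered, six steps are needed to reach 5.4. The 2.9 column matters because SAP 3.4.4 also reports response at the lower MID limit by visit.

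**Sum scores, other subscales unchanged.**
- A 15-point LymS step passes the TOI cutoff (15 > 11) and the FACT-Lym total cutoff (15 > 11.2). The 7.5-point step passes neither.
- A one-item step in PWB, SWB or FWB is 7/1 = 7, which just meets the FACT-G cutoff of 7. With two items it is 7/2 = 3.5 and does not.
- A one-item step in EWB is 6/1 = 6, below 7.

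**Fewest answers that still give a score.** One per subscale is enough: 5 of 42 for FACT-Lym total, 4 of 27 for FACT-G (7 + 7 + 6 + 7 = 27) and 3 of 29 for TOI (7 + 7 + 15 = 29).

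**Different items at the two visits.** The SAP does not require the same items to be answered each time. As a constructed example, suppose 14 LymS items score 2 and one scores 4 at baseline. LymS = (28 + 4) × 15/15 = 32. If only the last item is answered later, still at 4, LymS = 4 × 15/1 = 60. That is a gain of 28 points with no answer changed.

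**With at least half of the items answered (an assumed threshold).** The largest one-step changes are 15/8 = 1.875, 7/4 = 1.75 and 6/3 = 2.0. All are below the lower MIDs of 2.9 (LymS) and 3 (FACT-G).

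**The case against.** The appendix says a subscale is missing if all items are missing; it does not say only if. Section 3.11.1 addresses missing quality-of-life values specifically and leaves them to the instruments, as 3.4.4 does for scoring. If the developers' instructions contain a minimum-item rule, it could enter by that route, and one-item scores would never be computed. This stands in part. A reader might infer that the appendix overrides the deferral and that such scores will certainly be used. The SAP does not support that, because it ranks neither source above the other. Nor does the objection settle the matter the other way: the appendix is the only rule written out, 3.4.4 refers to it, and a programmer who follows it will score a one-item form.

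The effect is also confined to extreme forms. A single step makes a LymS responder at the main cutoff only with one or two of 15 items answered, and the arithmetic assumes the same items at both visits. PWB, SWB, EWB and FWB are not responder endpoints themselves, and a one-item EWB step does not reach the FACT-G cutoff. All of this stands.

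Finally, FACT-Lym is a secondary outcome in a single-arm study without hypothesis testing (Protocol Section 11), and completion rates will be tabulated. That is a fair reason to rank the point low. It is not a reason to leave two unreconciled rules in place.

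**Conclusion.** The point holds as an unreconciled scoring rule. Under the appendix as written, LymS can be scored from one or two items, and a one-step answer change then gives 15 or 7.5 points against a cutoff of 5.4. From three items upward a single step no longer suffices at that cutoff, although up to five items it still reaches the lower limit of 2.9.

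This rests on two assumptions: that the appendix is applied literally, and, for the one-step figures, that the same items are answered at baseline and follow-up. A reader might go further and infer that the reported responder rates or times to improvement will be materially distorted. The documents do not support that, since they give no rate of item non-response; the effect may be negligible. No primary or safety result depends on it. The change is desirable rather than essential.

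**What to change.** In SAP Appendix 16.1.9, replace the sentence on all items being missing with a minimum-item rule that matches the developers' instructions invoked in SAP 3.4.4 and 3.11.1. Put the same condition on scoring instruction 7. State that this rule governs scoring, the completion table and all derived endpoints.

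If the developers' instructions set no minimum, require at least half of the items: 8 of 15 for LymS, 4 of 7 for PWB, SWB and FWB, and 3 of 6 for EWB. This threshold is not in the documents and should be labelled as an assumption.

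The cost is an edit in two places of one appendix and slightly more missing subscale and total scores.
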